#### *Laboratory Abnormalities*

In the randomized clinical trial, Grade 1-4 neutropenia occurred in 15% of patients on enzalutamide (1% Grade 3-4) and in 6% of patients on placebo (no Grade 3-4). The incidence of Grade 1-4 thrombocytopenia was similar in both arms; 0.5% of patients on enzalutamide and 1% on placebo experienced Grade 3-4 thrombocytopenia. Grade 1-4 elevations in ALT occurred in 10% of patients on enzalutamide (0.3% Grade 3-4) and 18% of patients on placebo (0.5% Grade 3-4). Grade 1-4 elevations in bilirubin occurred in 3% of patients on enzalutamide and 2% of patients on placebo.

#### *Infections*

In the randomized clinical trial, 1.0% of patients treated with enzalutamide compared to 0.3% of patients on placebo died from infections or sepsis. Infection-related SAEs were reported in approximately 6% of the patients on both treatment arms.

#### *Falls and Fall-related Injuries*

In the randomized clinical trial, falls or injuries related to falls occurred in 4.6% of patients treated with enzalutamide compared to 1.3% of patients on placebo. Falls were not associated with loss of consciousness or seizure. Fall-related injuries were more severe in patients treated with enzalutamide and included non-pathologic fractures, joint injuries, and hematomas.

CONFIDENTIAL

This document is confidential. Do not disclose or use except as authorized.

### *Hallucinations*

In the randomized clinical trial, 1.6% of patients treated with enzalutamide were reported to have Grade 1 or 2 hallucinations compared to 0.3% of patients on placebo. Of the patients with hallucinations, the majority were on opioid-containing medications at the time of the event. Hallucinations were visual, tactile, or undefined.

## **6.2 Toxicity Management/Dose Modifications/Delays**

Enzalutamide is generally well-tolerated based on phase III data. Instructions on management of enzalutamide related toxicities > grade 2 (NCI CTCAE version 4) are detailed in section 6.0. Evidence of seizure will result in cessation of treatment with enzalutamide and withdrawal from the study. Management of other toxicities is detailed below.

- Grade 1-2 Toxicities: Management per investigator. No study treatment dose reduction indicated.
- Grade 3 or Higher Toxicities: Hold enzalutamide. Enzalutamide can be held for a maximum of 6 weeks. Hold will not affect assessment schedule. When toxicity resolves to  $\leq$  grade 1, resume at first dose modification level (120 mg daily). Prophylactic medications should be considered. If toxicity recurs, hold study medication and adjust or add medications to mitigate the toxicity. When recurrent toxicity has resolved to  $\leq$  grade 1, resume enzalutamide at 80 mg daily. If grade 3 toxicity recurs, the participant will be discontinued from the study.

Dose may NOT be re-escalated after it has been reduced.

CONFIDENTIAL

This document is confidential. Do not disclose or use except as authorized.

## 7. DRUG FORMULATION AND ADMINISTRATION

### 7.1 Enzalutamide

Refer to the package insert for enzalutamide information.

#### 7.1.1 Description

Enzalutamide is an androgen receptor inhibitor. The chemical name is 4-{3-[4-cyano-3-(trifluoromethyl)phenyl]-5,5dimethyl-4-oxo-2-sulfanylideneimidazolidin-1-yl}-2-fluoro-N-methylbenzamide.

The molecular weight is 464.44 and molecular formula is C21H16F4N4O2S.

#### 7.1.2 Mechanism of Action

Enzalutamide is an androgen receptor inhibitor that acts on different steps in the androgen receptor signaling pathway. Enzalutamide has been shown to competitively inhibit androgen binding to androgen receptors and inhibit androgen receptor nuclear translocation and interaction with DNA. A major metabolite, N-desmethyl enzalutamide, exhibited similar *in vitro* activity to enzalutamide.

Enzalutamide decreased proliferation and induced cell death of prostate cancer cells *in vitro*, and decreased tumor volume in a mouse prostate cancer xenograft model.

#### 7.1.3 Pharmacokinetics

The pharmacokinetics of enzalutamide and its major active metabolite (N-desmethyl enzalutamide) were evaluated in patients with metastatic CRPC and healthy male volunteers. The plasma enzalutamide pharmacokinetics are adequately described by a linear two-compartment model with first-order absorption.

##### *Absorption*

Following oral administration (enzalutamide 160 mg daily) in patients with metastatic CRPC, the median time to reach Cmax is 1 hour (range 0.5 to 3 hours). At steady state, the plasma mean Cmax values for enzalutamide and N-desmethyl enzalutamide are 16.6 µg/mL (23% CV) and 12.7 µg/mL (30% CV), respectively, and the plasma mean predose trough values are 11.4 µg/mL (26% CV) and 13.0 µg/mL (30% CV), respectively.

With the daily dosing regimen, enzalutamide steady state is achieved by Day 28, and enzalutamide accumulates approximately 8.3-fold relative to a single dose. Daily fluctuations in enzalutamide plasma concentrations are low (mean peak-to-trough ratio of 1.25). At steady state, enzalutamide showed approximately dose proportional pharmacokinetics over the daily dose range of 30 to 360 mg.

A single 160 mg oral dose of enzalutamide was administered to healthy volunteers with a high-fat meal or in the fasted condition. A high-fat meal did not alter the AUC to enzalutamide or N-desmethyl enzalutamide.

CONFIDENTIAL

This document is confidential. Do not disclose or use except as authorized.

#### *Distribution and Protein Binding*

The mean apparent volume of distribution of enzalutamide in patients after a single oral dose is 110 L (29% CV). Enzalutamide is 97% to 98% bound to plasma proteins, primarily albumin. N-desmethyl enzalutamide is 95% bound to plasma proteins.

#### *Metabolism*

Following single oral administration of  $^{14}\text{C}$ -enzalutamide 160 mg, plasma samples were analyzed for enzalutamide and its metabolites up to 77 days post dose. Enzalutamide, N-desmethyl enzalutamide, and a major inactive carboxylic acid metabolite accounted for 88% of the  $^{14}\text{C}$ -radioactivity in plasma, representing 30%, 49%, and 10%, respectively, of the total  $^{14}\text{C}$ -AUC0-∞.

*In vitro*, human CYP2C8 and CYP3A4 are responsible for the metabolism of enzalutamide. Based on *in vivo* and *in vitro* data, CYP2C8 is primarily responsible for the formation of the active metabolite (N-desmethyl enzalutamide).

#### *Elimination*

Enzalutamide is primarily eliminated by hepatic metabolism. Following single oral administration of  $^{14}\text{C}$ -enzalutamide 160 mg, 85% of the radioactivity is recovered by 77 days post dose: 71% is recovered in urine (including only trace amounts of enzalutamide and N-desmethyl enzalutamide), and 14% is recovered in feces (0.4% of dose as unchanged enzalutamide and 1% as N-desmethyl enzalutamide).

The mean apparent clearance of enzalutamide in patients after a single oral dose is 0.56 L/h (range 0.33 to 1.02 L/h).

The mean terminal  $t_{1/2}$  for enzalutamide in patients after a single oral dose is 5.8 days (range 2.8 to 10.2 days). Following a single 160 mg oral dose of enzalutamide in healthy volunteers, the mean terminal  $t_{1/2}$  for N-desmethyl enzalutamide is approximately 7.8 to 8.6 days.

#### 7.1.4 Form

Enzalutamide is a white crystalline non-hygroscopic solid. It is practically insoluble in water. Enzalutamide is provided as liquid-filled soft gelatin capsules for oral administration. Each capsule contains 40 mg of enzalutamide as a solution in caprylocaproyl polyoxylglycerides. The inactive ingredients are caprylocaproyl polyoxylglycerides, butylated hydroxyanisole, butylated hydroxytoluene, gelatin, sorbitol sorbitan solution, glycerin, purified water, titanium dioxide, and black iron oxide.

#### 7.1.5 Storage and Stability

##### *Pharmacy Storage Requirements*

The study treatment will be stored in a secure area and administered only to participants entered into the clinical study in accordance with the conditions specified in this protocol. Bottles of study treatment should be stored at a room

CONFIDENTIAL

This document is confidential. Do not disclose or use except as authorized.

temperature between 20°-25° C in a dry place and kept with container tightly closed.

*Storage Requirements for the Participant*

Bottles of study treatment should be stored at room temperature with the cap kept on tightly and should not be refrigerated. Participants should be advised to keep all medications out of the reach and out of sight of children.

Enzalutamide should not be handled by pregnant women.

7.1.6 Compatibility

Treatment with enzalutamide will be administered via oral capsules.

Enzalutamide is the only treatment agent which will be administered on the protocol.

7.1.7 Handling

There are no specific instructions for handling enzalutamide. Study treatment must only be dispensed by a Pharmacist or medically qualified staff. Study treatment is to be dispensed only to participants enrolled in this study. Once the study treatment is prepared for a participant, it can only be administered to that participant.

7.1.8 Availability

Enzalutamide capsules will be provided to each site. Participants will be provided with a 30-day supply to allow for visits to occur every 28 days with a  $\pm 3$  day window. Information presented on the labels for investigative product will comply with applicable local regulations. Site pharmacist will dispense the study treatment to each participant in accordance with this protocol under the guidelines of the site's dispensation standard operating procedure. The agent will be provided from commercial supply and will be provided free-of-charge.

7.1.9 Ordering

Enzalutamide is to be ordered from Astellas Pharmaceuticals or their designee. A drug order form as well as instructions on how to order study drug will be distributed to study sites prior to site activation.

7.1.10 Accountability

Accountability for study treatment is the responsibility of the investigator.

The study site must maintain accurate records demonstrating dates and amount of study treatment (enzalutamide) received, to whom dispensed (participant by participant accounting), and accounts of any study treatment accidentally or deliberately destroyed. At the end of the study, reconciliation must be made between the amount of study treatment supplied, dispensed, and subsequently destroyed.

CONFIDENTIAL

This document is confidential. Do not disclose or use except as authorized.

At the time of delivery of study treatment to the site, the investigator, designee, or Pharmacist (where appropriate) will confirm that the supplies for the study have been received. This following information will be confirmed: lot numbers, quantities shipped/delivered, and date of receipt.

#### 7.1.11 Destruction and Return

Drug should be destroyed at the site, after the sponsor– investigator approves the drug destruction policy at the site. Destruction will be documented in the Drug Accountability Record Form.

## 8. CORRELATIVE/SPECIAL STUDIES

Correlative studies will include analysis of prostate tumor from serial biopsies for AR modifications including AR sequence-mutations/splice variants, AR regulated gene expression, tumor androgen levels, profiling of enzymes involved in androgen synthesis and metabolism, and whole- exome and transcriptome sequencing. In addition, as an exploratory analysis we will analyze CTCs for mechanisms of AR resistance to include AR nuclear localization, AR sequencing, AR splice variant analysis and whole-exome and transcriptome sequencing. Lastly, we will analyze circulating tumor DNA for mechanisms of AR resistance to include AR sequencing and whole- exome and transcriptome sequencing. In addition, serum androgens will be measured. The correlative studies are required. A Laboratory Manual with instructions on sample collection and processing will be provided to study sites.

CTC research samples will be sent to the [REDACTED] at the University of Wisconsin for analysis purposes.

### 8.1 Statistical Data Analysis

Determination of biological and molecular endpoints to analyze possible AR related mechanisms of resistance to enzalutamide in serial tumor biopsies will occur as follows:

- AR sequencing
  - Mutations – continuous variable from microarray data
  - TMPRSS2:ERG translocation status – categorical variable from PT PCR (yes vs. no)
  - AR splice variants – categorical variable from RT PCR (native vs. alternative)
- AR regulated gene expression – continuous variable from microarray data
- Tumor androgen levels – continuous variable from mass spectroscopy data
- Profiling of enzymes involved in androgen synthesis/metabolism – continuous variable from microarray data

CONFIDENTIAL

This document is confidential. Do not disclose or use except as authorized.

- Whole-exome and transcriptome sequencing – continuous variable from sequencing analysis

Continuous data will be evaluated by calculating mean percent change in level. Categorical data will be evaluated by yes/no change in status. Ordinal/count number data will be evaluated by mean percent change in total count.

CONFIDENTIAL

This document is confidential. Do not disclose or use except as authorized.

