The AR is expressed at high levels in most cases of CRPC, with the AR gene being amplified in about one third of cases. Mutations in the AR that cause promiscuous activation by ligand have been detected in at least 15-40% of patients after development of resistance. Stranbrough and colleagues profiled the expression signatures of primary and metastatic prostate tumors, including both castration-sensitive and castration-resistant tumors, and found significant increased intratumoral expression of AR and genes converting adrenal androgens to testosterone and DHT in castrate-resistant tumors. Similarly, Montgomery *et al* showed that metastatic prostate cancers from anorchid men express transcripts encoding steroidogenic enzymes and maintain intratumoral androgens at concentrations capable of activating AR target genes and maintaining tumor cell survival.

Altered AR mRNA splicing and synthesis of truncated AR variant proteins lacking the AR LBD is another mechanism that has been postulated to drive overall resistance to

CONFIDENTIAL

This document is confidential. Do not disclose or use except as authorized.

ADT. Although many forms of these splice-variants are maladaptive and lead to a nonfunctioning AR protein, AR variants lacking the LBD but retaining the DBD and NTD are frequently expressed in CRPC metastases and high levels in prostate cancer tissue predict disease progression and shorter survival. AR splice-variant mutants can thereby be rendered insensitive to circulating or local hormone levels. Recently, it was shown the AR gene rearrangements expressing both full-length and AR variants are androgen independent and enzalutamide resistant.

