## 14. STATISTICAL CONSIDERATIONS

### 14.1 Primary Analysis

The primary objective of this trial is to analyze possible AR related mechanisms of resistance to enzalutamide in serial CRPC biopsies including AR sequencing (mutations, splice variants), AR regulated gene expression, tumor androgen levels, profiling of enzymes involved in androgen synthesis/metabolism, and whole-exome and transcriptome sequencing. These data are of various forms resulting in different measures for a given participant: (a) continuous data will be evaluated by calculating mean percent change in level, (b) ordinal data will be evaluated by the mean percent change in count, and (c) categorical binary data will be evaluated by No/Yes change in status.

For the primary analysis, only participants who received at least 2 cycles of enzalutamide and experienced progression will be eligible. We plan to enroll a total of 66 participants to obtain 40 evaluable participants. A 60% overall yield is based on the assumptions that 95% of participants are eligible, 90% of these participants have paired biopsies and 70% of participants have evaluable tumors for each sample.

The target sample size is based on power to evaluate a mean percent change in level. The hypothesis is that AR reactivation can lead to resistance to enzalutamide. We will evaluate the mean percent change in a set of resistance parameters using the paired t-test. All continuous variables will be evaluated as a set. A mean percent change of 30% would be considered biologically significant. The effect size is defined as the mean percent change divided by the standard deviation (SD) of percent change, which is unknown in this population. The table below provides the mean percent change that can be detected with 80% or 90% power under various scenarios of SD given a one-sided 0.025 alpha and 40 evaluable participants. For example, there is 80% power to detect mean percent change of 22.7% given a SD of 50% corresponding to an effect size=0.454 SD. The mean percent change presented ranges from 13.6%-31.5%. Therefore, this study is designed with satisfactory power to show a biologically significant mean percent change in a set of resistance parameters.

Paired Tumor Samples (n=40)				
	Paired t-test, 1-sided alpha=0.025			
Power=80%, Effect Size=0.454 SD				
Standard Deviation	30%	40%	50%	60%
Mean Percent Change	13.6%	18.2%	22.7%	27.3%
Power=90%, Effect Size=0.526 SD				
Standard Deviation	30%	40%	50%	60%

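### Section 8.1 types AR mutations as continuous microarray data analysed by percent change; if absence is scored 0, an acquired mutation has no computable value

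*Combined protocol and SAP*

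**What the plan says.** Section 8.1 assigns each laboratory measure a data type and gives each type an analysis rule.

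- Under the item "AR sequencing", mutations are entered as "Mutations – continuous variable from microarray data". The two neighbouring entries are categorical: TMPRSS2:ERG status (yes or no) and "AR splice variants – categorical variable from RT PCR (native vs. alternative". Whole-exome and transcriptome sequencing is also typed as continuous.
- The rule for the first type is "Continuous data will be evaluated by calculating mean percent change in level". A separate rule, with no baseline denominator, covers the second type: "Categorical data will be evaluated by yes/no change in status". The third rule goes back to a percentage of baseline: "Ordinal/count number data will be evaluated by mean percent change in total count".

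Section 14.1 repeats the three rules at participant level, including that "categorical binary data will be evaluated by No/Yes change in status". It takes all continuous variables together as a set, tests mean percent change with a paired t-test, and sizes the trial on the SD of percent change with 40 evaluable pairs. It does not itself assign mutations to a type; only the list in 8.1 does.

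Section 2.4 gives the only prevalence figure: AR mutations causing promiscuous activation by ligand "have been detected in at least 15-40% of patients after development of resistance".

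**The concern.** Mutations come first among the AR mechanisms listed in the primary objective (section 1.2), and the hypothesis in 14.1 is that reactivation of AR leads to resistance. The informative pattern for a mutation is therefore absent at baseline and present at progression. Percent change needs a non-zero baseline for each participant, so a rule built on it may have no value for exactly that pattern.

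The entry is also inconsistent in itself: an item listed under sequencing is given a microarray source and a continuous type. An analyst who follows the text would have to drop the affected participants or devise a rule after seeing the data, for a named component of the primary objective.

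**Working it through.** **1. The plan's own figure.** Inputs from 14.1: n = 40 pairs, one-sided alpha 0.025, paired t-test on percent change. Power = P(T > t critical), where T is noncentral t with df = 39 and noncentrality d x sqrt(40). Solving for d gives 0.4543 at 80% power and 0.5256 at 90%. Multiplying by SDs of 30, 40, 50 and 60% gives 13.6, 18.2, 22.7 and 27.3% (80% power), and 15.8, 21.0, 26.3 and 31.5% (90% power). Every cell of the table is reproduced. The table takes for granted that all 40 pairs yield a percent change.

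**2. The rule applied to a mutation.** Percent change = 100 x (progression - baseline) / baseline. With absence scored 0:

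| Baseline | Progression | Meaning | Percent change |
|---|---|---|---|
| 0 | 0 | never mutated | 0/0, undefined |
| 0 | 1 | acquired | division by zero |
| 1 | 0 | lost | -100% |
| 1 | 2 | increased | +100% |

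The rule records loss and cannot record acquisition. The same holds for an allele fraction, where absence is also 0.

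**3. Whether another branch helps.** The count branch also uses percent change, so it fails in the same way. The categorical branch needs no baseline denominator and has a value in all four rows. The documents give no offset, log transform or zero-baseline rule.

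**4. Illustrative size.** Assumption: baseline prevalence equals the 15-40% in section 2.4. Pairs with a defined value: 40 x 0.15 = 6 to 40 x 0.40 = 16. Pairs without: 40 - 16 = 24 to 40 - 6 = 34. Section 2.4 says at least, so these are upper figures.

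**5. Power for this variable taken alone, under the same assumption.** Using the calculation in step 1:

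| Defined pairs | Power at 0.454 SD | Effect detectable with 80% power | The same at SD 50% |
|---|---|---|---|
| 40 | 80% | 0.454 SD | 22.7% |
| 16 | 40% | 0.75 SD | 37% |
| 6 | 15% | 1.43 SD | 72% |

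**6. The categorical route.** All 40 pairs contribute. If k mutations are acquired and none lost, the exact one-sided McNemar p-value is 0.5^k: 0.5^5 = 0.031 and 0.5^6 = 0.0156. Six acquisitions with no losses would therefore fall below the plan's 0.025.

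**The case against.** **The division by zero is conditional.** It requires absence to be scored exactly 0, and the plan defines no scale. A raw microarray signal need not be 0 in a tumour without the mutation. This stands, and the point is worded accordingly. It does not rescue the entry: no such score is defined, and a signal intensity is not a mutation call.

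**The plan already has the right branch.** Section 14.1 includes a no/yes rule within the primary analysis, and the entry in 8.1 looks like a labelling slip. A reader might infer that mutations are shut out of the primary analysis altogether. The documents do not support that: the branch exists, and mutations have been assigned to the wrong one. The assignment is nevertheless what the text tells the analyst to follow.

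**The prevalence is borrowed.** The figure in 2.4 covers one functional class of AR mutation after resistance has developed and is stated as a minimum. It is not this trial's baseline. This stands in full, so steps 4 and 5 are illustrations.

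**Only one kind of variable is affected.** A reader might infer that 24 to 34 pairs are lost to the trial, or that the power table is wrong. Neither follows. Expression, tumor androgens and enzyme profiles from the same pairs can be analysed by percent change wherever baseline is positive, and the table is arithmetically correct.

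**Conclusion.** The plan is wrong as written on this entry. AR mutations are misclassified, and the rule they are sent to cannot count an acquired mutation if absence is scored 0, although it can score a lost one. That conclusion rests on the scoring of absence and does not depend on any prevalence figure.

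The number of pairs affected cannot be derived from the documents. On the assumption that baseline prevalence equals the background range, it is up to about 24 to 34 of 40, for the mutation variable only. The defect extends to exome variant calls and any other variable with zero baselines. It does not extend to strictly positive measures.

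**What to change.** In section 8.1, and with 14.1 aligned:

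- Retype AR mutations, and variant calls from exome sequencing, as categorical: present or absent at each biopsy, from sequencing.
- Reconcile the microarray source named for mutations with the sequencing planned elsewhere in the protocol.
- Analyse them under the existing no/yes change-in-status rule. Report acquired and lost mutations separately, each as a proportion of evaluable pairs with an exact confidence interval. An exact McNemar test is optional; because it sets losses against gains, it should not replace the separate reporting.
- If allele fraction is analysed, use absolute rather than percent change.

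The cost is a wording change in two sections, plus confirmation from the laboratory of which assay supplies the mutation calls. No added participants, biopsies or procedures are needed. The change should be made before paired results are examined.

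### AR splice variants, a named primary resistance mechanism, are reduced to an undefined binary RT-PCR item, so a rise in variant level in a tumour already positive at baseline may go unscored

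*Combined protocol and SAP*

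**What the plan says.** Splice variants are named in the primary objective (Sections 1.2 and 14.1). Section 8.1 lists them as a "categorical variable from RT PCR (native vs. alternative") and adds: "Categorical data will be evaluated by yes/no change in status". Section 14.1 repeats the rule: "categorical binary data will be evaluated by No/Yes change in status".

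The paired t-test and power table in Section 14.1 cover continuous variables only, with 40 evaluable participants and one-sided alpha 0.025. No test is named for paired binary items.

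Section 2.4 gives the biological background. It says that "AR variants lacking the LBD but retaining the DBD and NTD are frequently expressed in CRPC metastases" and that "high levels in prostate cancer tissue predict disease progression and shorter survival". It also says that "AR gene rearrangements expressing both full-length and AR variants are androgen independent and enzalutamide resistant".

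Section 5 places the first metastasis biopsy before treatment starts. Section 8.1 lists whole-exome and transcriptome sequencing as continuous, but defines no splice-variant summary from it.

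**The concern.** The background points to level as the informative quantity, while the coding keeps only a category. Two things are left open: how much variant makes a sample alternative, and where a sample with both full-length and variant AR belongs.

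The most natural reading of the coding is presence or absence. Under it, a tumour that already shows a variant before enzalutamide stays in the same category however far the level rises by progression. The participant is then counted as unchanged on a mechanism named in the primary objective. The more tumours are positive at baseline, the fewer participants can show a gain.

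As coded, the item also lies outside the only primary test that the plan names and powers.

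**Working it through.** **Inputs from the documents.** From Section 14.1: n = 40 pairs; one-sided alpha 0.025; detectable effect 0.454 SD at 80% power and 0.526 SD at 90%; biologically significant change 30%, with SD 50% as the worked example.

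**Inputs assumed.** Baseline positivity of 25%, 50%, 75% and 90% (Section 2.4 says only that variants are frequent); pre/post correlation 0.5, varied from 0.3 to 0.7; normally distributed log variant level; the alternative category read as level above a threshold; exact one-sided McNemar test at 0.025.

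**Step 1: reproduce the plan's figure.** Power = P(T > t(0.975, 39)), where T is noncentral t with 39 df and noncentrality d√40.
- Solving for 80% and 90% power gives d = 0.4543 and 0.5256. All eight table entries match (for example 0.454 × 50% = 22.7%).
- For a 30% change with SD 50%, d = 30/50 = 0.60 and power is 96%.

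The plan's calculation is correct for a continuous variable.

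**Step 2: what the binary item needs.** If all changes are gains, the one-sided p-value with m conversions is 0.5^m. Five give 0.031 and six give 0.016, so at least six are needed. The expected number able to convert is 40 × (1 − baseline positivity).

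| Baseline positive | Able to convert | Share of these that six represents |
|---|---|---|
| 25% | 30 | 20% |
| 50% | 20 | 30% |
| 75% | 10 | 60% |
| 90% | 4 | not attainable |

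**Step 3: power when the level rises across participants.** Correlated normal baseline and progression levels were simulated, shifted by d SDs of the change, and cut at the threshold that gives the stated baseline positivity (correlation 0.5).

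| Baseline positive | Binary, d = 0.454 | Signed-rank, non-detects tied, d = 0.454 | Binary, d = 0.60 |
|---|---|---|---|
| 25% | 34% | 50% | 59% |
| 50% | 37% | 65% | 60% |
| 75% | 24% | 75% | 38% |
| 90% | 6% | 77% | 7% |

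A paired t-test on a level measurable in every sample has 80% power at d = 0.454 and 96% at d = 0.60. Figures are approximate; repeat simulations differ by about one percentage point.

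Varying the correlation from 0.3 to 0.7 at d = 0.454 gives binary power of 24–42%, 28–44%, 17–28% and 3–7% across the four prevalences.

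**Step 4: power when resistance is new emergence only.** Suppose 30% of baseline-native tumours convert and none revert. The number of conversions is then binomial with n = 40 and probability 0.30 × (1 − baseline positivity), and power = P(at least 6). This gives 91%, 57%, 8% and 0.1% at 25%, 50%, 75% and 90% positivity.

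**The case against.** Several points on the other side have force.

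- **Other readings of the coding.** Classifying by predominant isoform or by a level cut-off also fits the wording. Either would place co-expressing samples, and a rise could then change category. The ceiling is therefore conditional on the presence/absence reading. What stands unconditionally is that the category is undefined.
- **Baseline positivity.** A reader might infer that the background shows these participants are often positive at baseline. It does not: Section 2.4 gives no percentage and no timing relative to enzalutamide. The inference is plausible, because CRPC metastases are what is biopsied and prior enzalutamide is excluded (Section 3.2.13), but it remains an inference.
- **Co-expression.** A reader might take Section 2.4 as showing that patients' tumours carry both forms. The study cited for that sentence is listed under a title describing cell-line work. It shows that the two forms are not exclusive in principle, not how often they coexist in biopsies.
- **Other data.** A reader might conclude that a rise would be invisible to the trial. Transcriptome sequencing of the same biopsies is planned as continuous, and CTC splice-variant expression is an exploratory objective (Section 1.4). Either could show it. The gap is that neither comes with a pre-specified splice-variant measure.
- **Size.** Comparing 80% with 34% overstates the loss at low positivity, because it assumes that every level is measurable. With non-detects tied, the comparison at 25% positivity is about 50% with 34%. If resistance is mainly new emergence and few tumours are positive at baseline, the binary item does well (91% in Step 4).

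Baseline-positive participants also stay in the denominator and can register a loss; what they cannot register is a gain.

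**Conclusion.** The point holds as a weakness of the planned splice-variant endpoint and should be corrected. The item lacks a threshold and a rule for mixed samples. Under the presence/absence reading, it cannot record a rise in a participant already positive at baseline.

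For a general rise in level, the quantitative measure had more power at every prevalence examined, even with non-detects tied. The margin at 0.454 SD runs from about 16 percentage points at 25% positivity (50% against 34%) to about 71 at 90% (77% against 6%). The direction is stable over the range examined. The size depends on assumed prevalence, correlation, test and reading of the category, none of which the documents fix.

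The documents do not support the stronger conclusions that the sample-size calculation is wrong or that the trial as a whole would miss a rise. The calculation reproduces; it simply does not cover this item.

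**What to change.** In Sections 8.1 and 14.1:

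1. Define a quantitative splice-variant measure per biopsy, from quantitative RT-PCR or the transcriptome data already planned. Report both the normalised variant transcript level and the variant-to-full-length ratio. The ratio alone can stay flat if full-length AR rises in parallel, and Section 2.4 lists increased AR expression as a proposed resistance mechanism.
2. Name one of the two in advance as the analysed parameter.
3. Analyse it within pair on the log scale, or by signed-rank test with non-detects tied at a stated detection limit.
4. Keep presence/absence as a supporting description of emergence among baseline-negative participants, with a defined positivity threshold and a rule for samples expressing both forms.

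The cost is wording and a little extra analysis; no further biopsy, visit or participant is needed. The downside is noisy values in low-expression samples, which is why the detection limit has to be stated beforehand.
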